10.1 Duration of Treatment

Participants may remain on study and continue to receive study product in the absence of unacceptable toxicity or withdrawal from study, intercurrent illness that prevents further participation, participant demonstrates an inability/refusal to comply with study procedures or, participant withdraws from study.

10.2 Compliance

Compliance is assessed in the laboratory by trained research assistants. As participants only use the study products on site in the laboratory, participant noncompliance with product use is expected to be negligible.

11 PROCEDURES INVOLVED

11.1 Participant Registration

Eligibility of each participant will be established prior to registration.

Informed consent MUST be completed prior to receiving any study related procedures.

11.2 Screening

Participants will be screened for eligibility and scheduled via telephone by the study coordinator.

Screening will take approximately 15 minutes. Please see **Appendix B1** and **Appendix B2** for specific screening questions.

There are up to 7 laboratory sessions of up to approximately 90 minutes each. Participants will be scheduled at their convenience with a minimum of 24 hours and maximum of 1 week (2 weeks if participant illness occurs) between sessions. See Table 1 for an overview of study measures/samples.

11.3 Session Procedures

Once a participant is identified as eligible, a visit date and time will be scheduled.

Participants will complete all experimental conditions, and are to abstain from vaping for a minimum of 30 minutes prior to the study session.

Roswell Park Protocol No.: I-3234822

The order of completion of Sessions 2-5 and 6-7 will be determined using Latin Square and A/B designs, respectively. Order of ad lib and directed bouts within a session will be determined by A/B designs.

Each laboratory session is expected to take approximately 90 minutes.

Directed vs. ad lib bouts. In the directed bout, participants are instructed to take a 4 second puff on the device every 60 seconds until a total of 8 puffs is reached. In the ad lib bout, participants are free to puff as they like for a defined 15 minute period.

Priming / Habituation Puff: At the beginning of each session, participants will take 1 priming puff and 1 habituation puff at a setting of 10 watts. If 10 watts is too harsh for the participant, wattage may be reduced by 2 until comfort level is obtained. Final wattage will be recorded and used throughout the session.

Session 1: Vaping topography using own-brand liquid

In this condition, we will use an A/B design to compare directed vs ad lib vaping of the participant's preferred product. After each bout, participants will complete a battery of sensory outcome measures. All questionnaires will be administered by the experimenter. Vape assembly and puffing regimen will also be directed by the experimenter. The device used will be a SmokTech® NORD2 or equivalent device. This session will be approximately 90 minutes long.

Sessions 2-5: Relationship of tobacco flavor formulation to vaping topography and sensory evaluation.

In this condition, we will use a 4 (flavor) x 2 (ad lib vs directed) within-subjects design. All liquids will have a 60/40 carrier concentration and 5% nicotine. Three commercial tobacco flavor variants versus one unflavored liquid (EC Blend) will be tested.

Over 4 laboratory sessions (sequence determined by Latin square), participants will complete ad lib and directed bouts (sequence determined by A/B design) using each flavor. After each vape, participants will complete a battery of sensory outcome measures. All questionnaires will be administered by the experimenter.

Vape assembly and puffing regimen will also be directed by the experimenter. The device used will be a SmokTech® NORD2 or equivalent device. These sessions will be approximately 90 minutes long.

Sessions 6-7: Relationship of nicotine formulation to vaping topography and sensory evaluation.

In this condition, we will use a 2 (nicotine form) x 2 (ad lib vs directed) within-subjects design. All liquids will have a 60/40 carrier concentration and 5% nicotine. The primary comparison is between 5% synthetic nicotine and 5% tobacco-derived nicotine.

Over 2 laboratory sessions (sequence determined by A/B design), participants will complete ad lib and directed bouts (sequence determined by A/B design) using each liquid form. After each vape, participants will complete a battery of sensory outcome measures. All questionnaires will be administered by the experimenter.

Vape assembly and puffing regimen will also be directed by the experimenter. The device used will be a SmokTech® NORD2 or equivalent device. These sessions will be approximately 90 minutes long.

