3 INCLUSION AND EXCLUSION CRITERIA

3.1 Inclusion Criteria

To be included in this study, subjects must meet the following criteria:

1. Age ≥ 21 and ≤ 55 years.
2. Current daily vapers of products containing nicotine.
3. No daily concurrent use of other tobacco products.
4. Self-reported general good health.
5. Women of childbearing potential must be willing to provide a urine sample and test negative prior to receiving any study-related products/procedures.
6. Ability to speak, read, and write in English.
7. Participant must understand the investigational nature of this study and sign an Independent Ethics Committee/Institutional Review Board approved written informed consent form prior to receiving any study related procedure.

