7 STUDY TIMELINES

Participants will complete up to 7 laboratory visits (approximately 1½ hour/visit) over about a 3 month period. Each visit will be scheduled a minimum of 24 hours and a maximum of 1 week apart. The time between visits may be extended up to 14 days (2 weeks) due to participant illness (e.g., COVID, influenza).

The total duration of the recruitment is 18 months with an approximate study completion date of 8-31-2024.

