11.4 Study Measures

Table 1 provides a summary of the study assessments and procedures.

Table 1 Study Measures

Reason	Measure	Visit	
		1	2-7
Indicators of individual differences	Phenylthiocarbamine (PTC)	1x / screening	
	6-n-Propylthiouracil (PROP)	1x / screening	
	Sodium benzoate tasting	1x / screening	
Pregnant or nursing females excluded from study participation	Urine pregnancy test for women of child bearing potential	1x / screening	
Preference Probes	Personal Food Taste Preferences	1x / session start	
Vaping Dependence	Penn State Dependence Scale	1x / session start	
Positive and Negative Affect	PANAS	1x / session start	1x / session start
Preference of large vs small reward	Delay Discounting	1x / session start	1x / session start
Base Sensory Measures	Self-Rated Sensory Ability	1x / session start	1x / session start
	Sensory e-cig Experiences Scale	1x / session start	1x / session start
	PROMIS-E	1x / session start	1x / session start
	SHRI-E	1x / session start	1x / session start
Sensory Impact	Generalized Magnitude Scale	2x / after each use	2x/ after each use

Reason	Measure	Visit	
		1	2-7
Upper airway sensation and subjective effects	Duke Sensory Scale	2x / after each use	2x / after each use
	Hedonic Attribute Profile	2x / after each use	2x / after each use
	Drug Liking Effects	2x / after each use	2x / after each use
	Product Evaluation Scale	2xs / after each use	2xs / after each use
Nicotine and Cotinine	Saliva	1x beginning of session & 2x / after each use	1x beginning of session & 2x / after each use
Oral microbiome assessment	Optional Oral Rinse Sample (Roswell Park Site only)	1x	

Sensory Acuity Screening

Prospective participants will complete phenylthiocarbamide (PTC), 6-n-propylthiouracil (PROP), and sodium benzoate tasting, commonly used indicators linked to individual differences (27), using manufactured, pre calibrated strips.

Urine

Female participants will be asked to urinate in a sterile 90-mL urine specimen container which will be tested for pregnancy.

Saliva Samples

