13 RISKS TO SUBJECTS

The potential risks to participants in the clinical studies, and their likelihood and seriousness, are described below

- Nicotine overdose: Some people who use nicotine products may experience symptoms of nicotine overdose such as nausea, sleep disturbance, headache, and vomiting; however, these symptoms are usually mild and temporary. Before nicotine products are used in human participants, they have undergone laboratory testing to assess the yields of nicotine present in the products; this will also provide quality control information to select the safest product.
 - The studies using nicotine products in participants will be performed in a clinical setting accustomed to monitoring for adverse events. The Principal Investigator and Co-Investigators have considerable experience with conducting outpatient studies

on novel nicotine delivery devices and their effects on participants and will be able to provide appropriate safety monitoring.

- Participants will be instructed that the investigational products are not to be ingested. If a product is ingested by mistake, the participants will be instructed to call the study physician [contact]). If they are experiencing serious symptoms of nicotine overdose, the participant should contact Poison Control or Emergency Medical Services.
- Nicotine withdrawal: Many individuals who quit smoking exhibit a pattern of symptoms related to withdrawal from tobacco use. These symptoms include: sadness and anxiety, irritability, anger, difficulty concentrating, appetite change and weight gain, insomnia, and decreased heart rate. Because participants in the studies will be asked to refrain from smoking overnight, it is likely that they will experience some of these symptoms. Consent forms will include sections describing the possibility of this occurrence. Study personnel will be trained to recognize these symptoms and educate the participants about them.
- Respiratory irritation: Some people who use ENDS (Electronic Nicotine Delivery Systems) may experience irritation of the mucosal membranes of the upper respiratory tract, but this may not be likely as they are already cigarette smokers. We will exclude participants or postpone procedures if they demonstrate chronic or acute respiratory problems.
- Inconvenience: It is possible that participants will experience inconvenience due to multiple study visits required.

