19.4 Primary Analysis

The primary objective is to evaluate the influence of:

Roswell Park Protocol No.: I-3234822

- a. tobacco flavoring composition on vaping topography
- b. synthetic vs. tobacco derived nicotine on vaping topography

The primary endpoints are measures of vaping topography, which are treated as quantitative outcomes and will be summarized by condition (flavor or nicotine composition) and bout (directed or ad-lib) using the appropriate descriptive statistics.

Using data from sessions 1-5, each endpoint will be modeled as a function of flavoring (own, none, and 3 commercial flavors), bout (directed or ad-lib), their two-way interaction, and random subject and site effects using a linear mixed model. Tests about the appropriate contrasts of model estimates will be used to compare:

- i) mean differences between flavors within a type of bout,
- ii) mean differences between bouts within a flavor,
- iii) effects of bout (ad lib – directed) between flavors,
- iv) effect of flavor between bouts.

Using data from sessions 6 & 7, each endpoint will be modeled as a function of nicotine composition (synthetic vs. tobacco derived), bout (directed or ad-lib), their two-way interaction, and random subject and site effects using a linear mixed model. Tests about the appropriate contrasts of model estimates will be used to compare:

- i) mean differences between composition within a type of bout,
- ii) mean differences between bouts within a composition,
- iii) effects of bout (ad lib – directed) between compositions,
- iv) effect of composition between bouts.

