Appendix B Study Screeners

Appendix B1: Core Eligibility Screener

Core Eligibility Screener

Name: _____

Preferred Phone Number _____

Type of phone: _____ Land Line _____ Mobile

If Mobile Phone, may we text you? _____ yes _____ no _____ only if necessary

1. Do you currently use tobacco products? By currently, we mean any use at all in the last month (30 days)

Yes (please proceed to question 2)
 No (please proceed to question 3)

2. Which tobacco products have you used in the past 30 days? Please check all that apply.

Cigarettes
 Cigars
 Cigarillos
 Clove Cigarettes
 Herbal Cigarettes
 Bidis
 Pipe Tobacco
 Roll Your Own
 Chewing Tobacco
 Moist Snuff
 Snus
 E-Cigarettes
 Vapes
 JUUL
 Nicotine pouches (i.e.: Zyn, On!, Velo)
 Nicotine gummies
 Nicotine gum
 Nicotine lozenges
 No products. I do not use tobacco or nicotine products.
(Please proceed to question 6)

3. Have you used tobacco or nicotine products in the past?

Yes (please proceed to question 4)
 No (please proceed to question 6)

Roswell Park Protocol No.: I-3234822

4. What products did you use? Please check all that apply.

- Cigarettes
- Cigars
- Cigarillos
- Clove Cigarettes
- Herbal Cigarettes
- Bidis
- Pipe Tobacco
- Roll Your Own
- Chewing Tobacco
- Moist Snuff
- Snus
- E-Cigarettes
- Vapes
- JUUL
- Nicotine pouches (i.e.: Zyn, On!, Velo)
- Nicotine gummies
- Nicotine gum
- Nicotine lozenges

5. How long ago did you quit smoking?

- More than a year ago
- Less than a year ago
- Less than 6 months ago
- Less than a month ago

6. Have you used any Nicotine Replacement medication such as the patch, gum, lozenge, spray, or inhaler in the past 30 days?

- Yes
- No

7. Do you smoke cigarettes some days or every day?

- Some Days
- Every Day
- Not at all

8. How many cigarettes do you smoke per day? Please enter a number.

9. How long have you been smoking?

- More than 1 year
- Less than 1 year
- Not at all

Roswell Park Protocol No.: I-3234822

10. Have you tried to quit smoking in the past 30 days?
(more than a 24 hour time period without smoking)

- Yes
- No
- Not a smoker

11. Are you seriously thinking of quitting smoking?

- Yes, within the next 30 days
- Yes, within the next 6 months
- No, not thinking of quitting
- Not a smoker

12. How would you describe your gender identity? (for demographics purposes, only)

- Male
- Female
- Trans-male
- Trans-female
- A different gender identity not listed above

13. What is your age? Please enter a number (years).

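### Nicotine state at session start can differ between one participant's sessions and is already sampled in saliva, but the models leave it out, and Sections 11.3 and 13 disagree on pre-session abstinence

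*Combined protocol and SAP*

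**What the plan says.** **Abstinence.** Under 11.3, participants "are to abstain from vaping for a minimum of 30 minutes prior to the study session". That is a floor on vaping only, with no ceiling and no stated check. Section 13 explains why withdrawal symptoms are expected in different terms: "Because participants in the studies will be asked to refrain from smoking overnight". Section 11.2 lets sessions be booked to suit the participant.

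**Other nicotine.** Inclusion criterion 3 in 3.1 reads "No daily concurrent use of other tobacco products", so non-daily use is allowed. The core screener (Appendix B1) asks "Have you used any Nicotine Replacement medication such as the patch, gum, lozenge, spray, or inhaler in the past 30 days", but 3.2 does not name nicotine replacement as an exclusion.

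**Spacing and order.** Section 7 states: "Each visit will be scheduled a minimum of 24 hours and a maximum of 1 week apart". Section 19.2 randomizes liquid order in sessions 2-5 and in sessions 6-7. Session 1 (own brand) always comes first.

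**Saliva.** Table 1 in 11.4 schedules saliva "1x beginning of session & 2x / after each use" at every visit, and the text of 11.4 plans a nicotine assay. The only analytic use given is the nicotine boost in Section 16.

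**Model.** Section 19.4 fits flavoring or nicotine composition, bout, "their two-way interaction, and random subject and site effects using a linear mixed model". Section 19.5 reuses these models for sensory measures. The only candidate covariates named (11.4, Other Questionnaires) are affect and food taste preferences, for sensory ratings.

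**The concern.** A participant may arrive half an hour after vaping for one liquid and many hours after for another, or after using a pouch or nicotine gum on one day and not on the other. All of these satisfy 11.3. If recent nicotine intake affects how someone puffs in a free 15-minute bout, or how they rate liking and irritation, the variation enters the comparison of liquids. A random subject intercept absorbs a person's usual level but not the departure from it on a given day.

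What is at stake is efficiency in a small trial. Section 19.1 expects only 38 to 53 completers at session 7, when the synthetic versus tobacco-derived comparison is completed. The plan pays for a measurement of the nuisance variable at every session and then does not use it in the primary or secondary models.

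**Working it through.** **Inputs from 19.1:** 72 participants, 5-10% attrition per session, two-sided paired t-test, alpha 0.05, 80% power, detectable differences 0.47 SD (n = 38) and 0.39 SD (n = 53).

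**Step 1: reproduce the plan's figures.** Completers at session 7 are 72 × 0.95^6 = 52.9 and 72 × 0.90^6 = 38.3, matching 53 and 38. The noncentral t with n − 1 degrees of freedom and noncentrality d√n gives detectable differences of 0.467 (n = 38) and 0.392 (n = 53). Power at the stated 0.47 and 0.39 is 80.5% and 79.6%. The figures are sound and, being in SD units, do not depend on the abstinence rule.

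**Step 2: gain from adjustment.** Let ρ be the within-person correlation between log session-start saliva nicotine and the outcome. The documents give no value, so 0.2 to 0.5 is an assumption; if ρ is zero there is no gain. Residual variance is multiplied by 1 − ρ², the equivalent sample is n/(1 − ρ²), and the detectable difference is multiplied by √(1 − ρ²), provided the planning SD already contains this variance.

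| ρ | Variance cut | Equivalent of 53 | Equivalent of 38 | Detectable difference, n = 53 | n = 38 |
|---|---|---|---|---|---|
| 0.2 | 4% | 55.2 (+2) | 39.6 (+2) | 0.38 | 0.46 |
| 0.3 | 9% | 58.2 (+5) | 41.8 (+4) | 0.37 | 0.45 |
| 0.5 | 25% | 70.7 (+18) | 50.7 (+13) | 0.34 | 0.41 |

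**Step 3: cost of estimating the slope.** For a two-session contrast with a roughly normal covariate, the variance rises by a factor of about 1 + 1/(n − 3): 1 + 1/50 = 1.020 at n = 53 and 1 + 1/35 = 1.029 at n = 38. At ρ = 0.2 the net variance ratio is 0.96 × 1.020 = 0.979 or 0.96 × 1.029 = 0.988, so most of the gain goes at n = 38. At ρ = 0.5 it is 0.765 or 0.772, so most of the gain stays.

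**Step 4: if the planning SD left this variance out.** The plan gives no SD in raw units, so this cannot be ruled out. If an assumed share r² of the paired-difference variance is extra and unmodelled, power is that at d√(1 − r²). For n = 38 and n = 53 it is 78.5% and 77.5% at r² = 5%, 76.3% and 75.3% at 10%, and 65.6% and 64.5% at 30%.

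**Step 5: which comparisons are exposed.** Section 10 fixes 8 puffs of 4 seconds at 60-second intervals in the directed bout, so directed puff count and timing have little room to respond. Ad lib topography and subjective ratings do. Comparisons of liquids cross sessions and carry the variation. Comparisons of bouts within one liquid share a session start.

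**Step 6: is the sample unaffected by the study liquid?** Section 11.3 places a priming puff and a habituation puff at the beginning of each session. Appendix E puts saliva at −15 minutes and does not show those puffs, so their order is not stated.

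**The case against.** The strongest reply is that this is an optional efficiency gain in a randomized within-subject design. Arrival state is ordinary residual noise, chance imbalance is already covered by the standard error, and ρ is assumed. At ρ of 0.2 to 0.3 the detectable difference at n = 53 moves only from 0.39 to about 0.38 or 0.37. A short abstinence also suits a study of how daily vapers actually use products. All of this stands and limits the point to precision.

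Four stronger readings are tempting, and the documents do not support them.

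- That study liquids are separated by a 30-minute washout. Visits are at least 24 hours apart (Section 7); the 30 minutes concerns the participant's own vaping.
- That someone who smokes on the way in clearly complies. Section 13 says participants will be asked not to smoke overnight. For smoking, the defect is that 11.3 and 13 conflict. For pouches and nicotine replacement, neither section says anything.
- That the screener shows a dropped exclusion for nicotine replacement. Appendix B1 is a departmental screener serving several studies, and the study-specific one (Appendix B2) asks about daily use of other tobacco, in line with 3.1.
- That the liquid contrasts are biased. Order is randomized within sessions 2-5 and within 6-7 (19.2).

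The reply does not remove the remaining fact: a baseline measured at every session is left out of the models, and nothing else in the plan takes its place.

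**Conclusion.** The point holds as a matter of precision. Session-start nicotine can vary within a person under the rules as written, the subject effect does not remove that variation, and the saliva measure is absent from 19.4 and 19.5. For randomized contrasts the cost is wider intervals, mainly for ad lib topography and ratings. Bias is more plausible for own-brand contrasts, because session 1 is unrandomized and always first yet enters the flavor model; a saliva covariate would remove at most part of that.

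The size rests wholly on the assumed ρ. It is about 2 completers at ρ = 0.2 on either base, and 18 on 53 or 13 on 38 at ρ = 0.5, before the slope-estimation cost. The gain may be negligible or useful, and the documents cannot say which. A reader might infer that the covariate would correct the problem in full. It would adjust only in part, and one value per session says nothing about carry-over from bout 1 to bout 2, which Appendix E starts 30 minutes after bout 1 ends. The plan's sample-size figures are not in error.

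**What to change.** (a) In 19.4 and 19.5, prespecify log session-start saliva nicotine as a fixed covariate. Split it into the participant's mean over the sessions in that model and the session's deviation from that mean. Use only the sample before bout 1, and state that it is taken before the priming and habituation puffs. Add a simple rule for missing or failed assays and, because the value is logged, for results below the assay limit.

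(b) Reconcile Sections 11.3 and 13 on the pre-session abstinence requirement and on which products it covers. The choice of rule is for the investigators. Whatever they decide, record the type and time of last nicotine use at session start.

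The cost is one model term in two parts, two questions per session and a wording correction. The sample and the nicotine assay are already planned, and randomization is untouched. The downsides are the missing-assay rule and the few percent of variance spent on estimating the slope.

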11.4 Study Measures

Table 1 provides a summary of the study assessments and procedures.

Table 1 Study Measures

Reason	Measure	Visit	
		1	2-7
Indicators of individual differences	Phenylthiocarbamine (PTC)	1x / screening	
	6-n-Propylthiouracil (PROP)	1x / screening	
	Sodium benzoate tasting	1x / screening	
Pregnant or nursing females excluded from study participation	Urine pregnancy test for women of child bearing potential	1x / screening	
Preference Probes	Personal Food Taste Preferences	1x / session start	
Vaping Dependence	Penn State Dependence Scale	1x / session start	
Positive and Negative Affect	PANAS	1x / session start	1x / session start
Preference of large vs small reward	Delay Discounting	1x / session start	1x / session start
Base Sensory Measures	Self-Rated Sensory Ability	1x / session start	1x / session start
	Sensory e-cig Experiences Scale	1x / session start	1x / session start
	PROMIS-E	1x / session start	1x / session start
	SHRI-E	1x / session start	1x / session start
Sensory Impact	Generalized Magnitude Scale	2x / after each use	2x/ after each use

Reason	Measure	Visit	
		1	2-7
Upper airway sensation and subjective effects	Duke Sensory Scale	2x / after each use	2x / after each use
	Hedonic Attribute Profile	2x / after each use	2x / after each use
	Drug Liking Effects	2x / after each use	2x / after each use
	Product Evaluation Scale	2xs / after each use	2xs / after each use
Nicotine and Cotinine	Saliva	1x beginning of session & 2x / after each use	1x beginning of session & 2x / after each use
Oral microbiome assessment	Optional Oral Rinse Sample (Roswell Park Site only)	1x	

Sensory Acuity Screening

Prospective participants will complete phenylthiocarbamide (PTC), 6-n-propylthiouracil (PROP), and sodium benzoate tasting, commonly used indicators linked to individual differences (27), using manufactured, pre calibrated strips.

Urine

Female participants will be asked to urinate in a sterile 90-mL urine specimen container which will be tested for pregnancy.

Saliva Samples

Saliva samples will be collected before and after product use in both session using a Salimetrics SalivaBio Passive Drool method (https://salimetrics.com/collection-method/passive-drool-salivacollection_ device/). This method involves unstimulated collection of whole saliva which will be passively drooled into a cryovial until ~1.8mL of saliva is collected. Samples will be divided into aliquots and frozen at -20 C. Saliva will be tested for nicotine using a GC-qTOF-MS method. Saliva will be further tested for stress markers of cortisol (<https://salimetrics.com/assay-kit/salivary-cortisol-elisa-kit/>) and DHEA (<https://salimetrics.com/assay-kit/salivary-dhea-elisa-kit/>) and proinflammatory cytokines of IL-6 (<https://salimetrics.com/assay-kit/salivary-il-6-elisa-kit/>) and IL-1b (<https://salimetrics.com/assaykit/salivary-interleukin-1-beta-elisa-kit/>). Color intensity will be read at 450nm using a plate reader (BioTek). The integrated values of known standards will be used to generate a standard curve. Density values for unknown samples will be determined by interpolation from the standard curve for each analyte to calculate concentrations in pg/mL saliva. Saliva samples may also be used to test for nicotine and cotinine levels using similar methods to blood analyses. Additional details about the processing of saliva samples are

Roswell Park Protocol No.: I-3234822

provided in **Section 15**. A full description of the sample collection procedure can be found in **Appendix D**.

Optional Oral Rinse Sample (Roswell Park site only)

Oral rinse samples will be collected using a rinse & gargle method with Scope mouthwash, which will be stored in a -80°C freezer and kept at Roswell Park for analysis. We will characterize the microbiota by analyzing 16S rRNA (bacteria) and ITS1 gene (fungi) and the virome (including human papillomaviruses) using NGS. We will also complement analyses with functional information obtained through Bioinformatic algorithms (PICRUSt) and shotgun metagenomics. This approach will quantify differences in secreted and other microbial gene products; connect them to annotated pathways and make them available for downstream analyses. Thus, we will analyze inferred biochemical functions that are related to inflammation and subsequent oral and respiratory outcomes. Additional details about the processing of oral cell samples are provided in **Section 15**. A full description for oral rinse sample collection is provided in **Appendix D**.

eTop Vaping Topography

The eTop (American University of Beirut) is a mouthpiece-based desktop device designed to measure e-cigarette puff topography. eTop mouthpieces can be adapted for various e-cigarette designs. The eTop continuously monitors, digitizes, and records airflow through the mouthpiece that is connected to an e-cigarette. A puff is detected by a pressure transducer whenever changes in pressure occur across an orifice that is incorporated into the mouthpiece (e.g., when user begins to inhale). Orifice dimensions and transducer sensitivity provide valid measurements at puff flow rates as low as 3ml/sec. The signal from the transducer is digitized using a National Instruments data acquisition device (NI DAQ USB-6008) and communicated to the computer via USB. Data are stored offline by an associated computer application that communicates with the eTop device. Based on the start and end time of every puff, the total number of puffs detected, and the volume of each puff detected, the average puff duration (sec), interpuff interval (sec), puff volume (mL), and puff flow rate (mL/s) are computed. The eTop has been shown to capture topography data with high validity and reliability and does not interfere with natural e-cigarette puffing behavior (Feliciano et al., 2020 (28)).

Sensory Measures

The product evaluation scale, Duke Sensory Scale, and Hedonic Attribute Profile will be used to examine different aspects of upper airway sensation and subjective effects. A labeled generalized magnitude scale will be used to score sensory impact. The sensory e-cig experiences scale; PROMIS-E; SHRI-E are also assessments that will be used. Refer to **Appendix C**.

Purchase Decision Making

We will administer a 5-trial adaptive delay discounting task, implemented in REDCap, to assess user preference for smaller immediate rewards over larger delayed rewards (i.e., delay discounting). This interactive instrument automatically adjusts to respondents' choices to produce a k -parameter after five trials. Participants are asked on the first trial whether they would prefer to receive \$500 now or \$1,000 in 3 weeks. If the immediate choice is selected (\$500 now), then the second trial shortens the delay (i.e., choice: \$500 now or \$1,000 in 1 day). If the delayed option was chosen on the first trial (\$1000 in 3 weeks), then the second trial lengthens the delay (i.e., \$500 now or \$1000 in 2 years). All subsequent trials are adjusted based on responses from the preceding trial. The k -parameter is expressed as the natural logarithm of k in a hyperbolic model,

Roswell Park Protocol No.: I-3234822

with k increasing as the preference for smaller sooner rewards increases.(29) Additional items probe participants' reliance of various sources of information that may influence purchases.

Other Questionnaires

The PANAS is administered to probe current balance of positive and negative affect. Additional items probe personal food taste preferences. All of these will be explored as potential covariates for sensory ratings. The Penn State Dependence Scale will evaluate vaping dependence. Refer to **Appendix C**.

